5.2. Inclusion criteria

Study number: EUP/HED/008/2016

VERSION DATE: 21.11.2016

Each study participant must meet the following criteria:

- Patient of either sex, aged 2 to 12
- Diagnosis of a productive (wet) cough of various aetiology

The inclusion into the Study will take place during the 1st visit. Only Patients in which the earlier recommendation to use HEDUSSIN® in the therapy of productive cough of various aetiology was made due to solely medical reasons and independently from this Study, and who did not take the first dose of the syrup at the moment of the inclusion, are eligible. The inclusion of the patient into the group where the given treatment method is used should not result from the study protocol. It should be dependent solely on the current medical practice and remain in accordance with the current medical knowledge.

5.3. Exclusion criteria

Patients meeting the following criteria will not be included in the study:

- 1. Patients under the age of 2 and above the age of 12 years.
- Hypersensitivity to the active substance ivy leave extract; to other plants from the Araliaceae family or to the excipients (non-crystallizing liquid sorbitol, potassium sorbate, xanthan gum, anhydrous citric acid).
- 3. Concomitant treatment with corticosteroids, beta-2 mimetics, theophylline or other medicine that may inhibit the coughing reflex during the 7 day period prior to the inclusion into the Study.
- Neoplastic diseases of the respiratory system.

5.4. Procedures for treatment discontinuation or if the patient withdraws from the study

If the patient is excluded from the Study (i.e. they discontinue the participation in the Study before the evaluations schedule in the Assessment Protocol), the main reason for discontinuation will be recorded in the Study Questionnaire (SQ). Discontinuation from the study due to adverse effects must be adequately described in the patient records.

The investigator provides patients excluded from the study with adequate further treatment - personally or by another doctor with the existing documentation of the disease course.

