6. METHODOLOGY

6.1. Schedule of the Study

A summary of observations and assessments that will be conducted during the study is presented in the following table.

Table1. Schedule of the assessments during the Study realisation

PROTOCOL FOR A NON-

INTERVENTIONAL

STUDY

Procedures for particular assessments	Visit 1*	Visit 2*
Demographic data	Х	
Qualification of the Patient into the PAES Study (inclusion criteria)	Х	
History concerning comorbidities and their treatments	Х	Х
Basic diagnosis and its duration	Х	
The dose of the medicinal product used		Х
The assessment of :		
 The symptoms associated with the respiratory system (BSS scale) 		
Assessment of the body temperature	Χ	Х
Assessment of the overall wellbeing (VAS scale)		
Assessment of the sleep quality disturbances		
The use of concomitant treatment		
Duration of the infection (number of days)		Х
Reporting adverse effects related to the HEDUSSIN ® medicinal product use		Х

^{*}The assessments will take place as part of the routine Patient observation

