9. REPORTING RELATED ADVERSE EFFECTS

If a related adverse event occurs, the Investigator is obliged to report each observed event by completing the DRUG RELATED ADVERSE EVENT REPORT and sending it in accordance with the Law on Medicinal Products to:

Phytopharm Kleka S.A. And

URPL

Study number: EUP/HED/008/2016

VERSION DATE: 21.11.2016

Should any severe adverse drug reaction occur, these should be reported within 24h.

The Investigator may additionally report the drug related adverse event to the Study Organizer through the **www.dzialanianiepozadane.com** website. The events reported to the Study Organizer via the abovementioned platform are forwarded to the URPL.

The addresses of all parties are available below:

Phytopharm Kleka SA, [name]

[name] and [name] (deputy) — Persons responsible for the pharmacotherapy safety on behalf of the Sponsor.

e-mail: [contact]

[contact]

Department for Monitoring of Adverse Action Medicines, Office for Registration of Medicinal Products, Medical Devices and Biocidal Products (URPL)

[name]

[name]

tel.: [name]

fax: [name]

e-mail: [contact]

Study Organizer Office: Europharma M.Rachtan Sp.z o.o.

[name]

Reporting via the platform: www.dzialanianiepozadane.com

The procedure for reporting ADR will be carried out in accordance with the standards of GVP

Reporting of adverse reactions associated with the use of the **HEDUSSIN**® medicinal product will be carried out in accordance with the provisions of the Pharmaceutical Law, in particular with art. 45 of the Act on professions of physicians and dentists.

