10.4.3. Adverse effects analysis

This Study is an efficacy assessment study (PAES) and its main aim is not focused on the research of the medicinal product safety – especially, the analysis of the reported adverse events will be conducted in a general manner as an auxiliary analysis in relation to the main aim of the Study, i.a. the efficacy assessment. The details on the safety of the used treatment contained within the Study Questionnaires will be included in the summaries of data on individual patients. Analysis and summary tables will be based on data from the study population taking into account the duration of exposure to the medicinal product under investigation.

All adverse effects will be coded in accordance with Medical Dictionary for Regulatory Activities (**MedDRA**).

The prevalence of all reported adverse effects and severe adverse effects occurring during the study will be presented in the form of tables.

In addition, summary tables will be presented, that will include data the maximum intensity of the adverse effect, the relationship to the study drug administration and related data on adverse effects as well as patients who discontinued treatment with the study drug due to the occurrence of adverse effects.

It is considered that related adverse effects occurring during the use of the study drug are any adverse effects that occur during an active study phase if:

They were not present prior to the first dose of study medication

or

• They were present prior to receiving the first dose of study drug, but its severity has been increasing during the observation.

All adverse effects occurring during the use of the study drug will be noted in the tables of adverse effects. Other medications used to treat concomitant diseases will be coded in accordance with the WHO Medication Coding Dictionary and will be summarized with the number and percentage of patients receiving concomitant medications and these patients will be grouped according to the pharmacological class of the medicine and International Non-proprietary Name (INN) of the drug.

10.5. Factors which may affect the statistical analysis and modify the results of the Study

- The Patients failure to report on the scheduled control visit
- The discontinuation of the study drug use for reasons other than adverse effects,
- Use other drugs during observation,

Study number: EUP/HED/008/2016

VERSION DATE: 21.11.2016

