12.3. Verification of the source data

STUDY

Not applicable.

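### For a child who leaves before Visit 2, no stated route assures that adverse-effect detail reaches the study database, so the Section 10.4.3 frequency and intensity tables risk being biased low

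*Protocol*

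**What the plan says.** All references are to the Protocol.

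- **Section 6.1, Table 1.** The row "Reporting adverse effects related to the HEDUSSIN ® medicinal product use" is marked at Visit 2 only. The itemised Visit 2 list in Section 6.2.2 does not mention adverse effects.
- **Section 5.4.** For a child who leaves early, the main reason goes into the Study Questionnaire. The next sentence reads "Discontinuation from the study due to adverse effects must be adequately described in the patient records".
- **Section 9.** When a related event occurs, "the Investigator is obliged to report each observed event by completing the DRUG RELATED ADVERSE EVENT REPORT". The form goes to the company and URPL. For the body that handles the study data, the wording is permissive: "The Investigator may additionally report the drug related adverse event to the Study Organizer". Section 3.2 is looser still and lists the company, URPL and the Organizer as alternatives.
- **Sections 12.3, 12.5 and 13.3.** Section 12.3, "Verification of the source data", is marked as not applicable. The Organizer manages the data and prepares the report.
- **Sections 10.4.2 and 10.4.3.** Reasons for leaving are tabulated. Adverse effects are to be MedDRA-coded and tabulated by frequency, maximum intensity and relationship to the drug, with a summary of "patients who discontinued treatment with the study drug due to the occurrence of adverse effects". These tables rest on the study population. Section 10.2 restricts only the efficacy analysis to children with all assessments.
- **Section 10.6.** The safety analysis is said to allow the frequency of effects occurring in more than 1 in 1000 to be assessed.

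**The concern.** Section 10.4.3 promises coded events with intensity and relationship for the whole study population. The collection rules secure those items only for children who reach Visit 2. If intolerance is one of the reasons for leaving early, the gap is selective: events in children who stay are recorded in full, while events in children who leave depend on optional steps. Because the denominator includes the leavers, a child whose event never arrives is counted as event-free. The frequency claim in Section 10.6 then rests on incomplete numerators, and Sections 1.3 and 3.3 say that the study data will be used in marketing and training.

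**Working it through.** The documents give no adverse-effect count or withdrawal rate to reproduce. The check is a trace of the data path, followed by an illustration.

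**Step 1. What reaches the Organizer under the stated rules**

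| Child with an adverse effect | Required in the questionnaire | Other route | Result |
|---|---|---|---|
| Attends Visit 2, whether or not the syrup was stopped | Adverse effect (Table 1) | Section 9 report | Captured |
| Leaves before Visit 2, effect is the main reason | Main reason only (5.4) | Patient records; Section 9 report to company and URPL; copy to Organizer optional | Can be counted as a discontinuation; term, intensity and relationship not assured |
| Leaves before Visit 2, another main reason | The other reason only (5.4) | Section 9 report if the event is observed and considered related; copy to Organizer optional | May not appear at all |

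No section requires the Section 9 reports to be reconciled with the study database.

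**Step 2. How the loss acts on a tabulated rate**

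Inputs:
- N = 500 (Section 10.3). Section 5.1 also gives 3000 in one sentence, but the percentages that use all enrolled children do not depend on N.
- p = true proportion affected. Assumed 5%, inside the 1% to 10% band that Section 1.2 labels common.
- e = share of affected children who leave before Visit 2. Not given.
- u = share of those whose event detail is not recovered through a query, an optional copy or the company. Not given.

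Formulas: f = e × u, and tabulated rate = p × (1 − f).

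With p = 5%, the number affected is 500 × 0.05 = 25:

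| f (assumed) | Events tabulated | Rate on 500 |
|---|---|---|
| 0% | 25 | 5.0% |
| 20% | 25 × 0.80 = 20 | 4.0% |
| 25% | 25 × 0.75 = 18.75 | 3.75% |
| 50% | 25 × 0.50 = 12.5 | 2.5% |
| 75% | 25 × 0.25 = 6.25 | 1.25% |

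At f = 50%, the ends of the common band give:
- p = 1%: 5 × 0.5 = 2.5 events, or 0.5%
- p = 10%: 50 × 0.5 = 25 events, or 5%

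A true 1% tabulated as 0.5% would fall from the common to the uncommon band of Section 1.2.

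Removing the lost children from the denominator hardly helps: 12.5 / (500 − 12.5) = 2.56%, against 2.5%.

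**Step 3. Limits of f**

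f is zero if every early leaver's event is recovered. It cannot exceed e, and equals e only if every optional route fails. With e = 50% and half of those recovered, f = 0.5 × 0.5 = 25%, and the tabulated rate is 3.75%. These rates concern codable events in the frequency and intensity tables, not the count of discontinuations.

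**The case against.** A reader might infer that children who quit because of intolerance are absent from the adverse-effect tables altogether. The text does not support that. Section 5.4 puts the main reason in the questionnaire, Section 10.4.2 tabulates those reasons, and Section 10.4.3 plans a summary of discontinuations due to adverse effects. A child whose main reason was an adverse effect can be counted there.

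A reader might also infer that the additional aim, tolerance, receives a falsely good answer. Section 2.2 defines tolerance by sleep disturbance, weakness and the wellbeing VAS, not by adverse-effect counts, and Section 10.4.3 calls the adverse-event analysis auxiliary. This point does not reach those measures.

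Four further arguments deserve weight:

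- **Stopping the syrup is not leaving the study.** Nothing says that a child who stops forfeits Visit 2. This stands, and it confines the point to children who leave before that visit.
- **Queries.** Under Sections 11 and 12.4 the Organizer checks questionnaires and the investigator must answer queries. An exit reason of adverse effect with no event described could well prompt one. This gives partial recovery. It does not help when another reason is recorded, because no adverse-effect entry is then required and nothing looks incomplete.
- **Section 9 is not tied to a visit.** This is true, and it serves pharmacovigilance. It covers related events only and does not oblige anyone to deliver the report to the Organizer.
- **The questionnaire is not shown.** Its exit page may ask for event detail. If so, the gap is one of protocol wording, but the Protocol itself does not require it.

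**Conclusion.** The concern holds as a gap in the data path. For children who leave before Visit 2, the Protocol assures the Organizer of the main reason for leaving and nothing more about an adverse effect. The Section 10.4.3 frequency and intensity tables, and the Section 10.6 claim built on them, are therefore at risk of a downward bias. The direction rests on the plausible assumption that at least some affected children leave early and that not all of their events are recovered. The size cannot be estimated from the documents: the illustrated fall from 5% to between 3.75% and 1.25% follows from an assumed loss of 25% to 75%, and is not a forecast. The matter does not affect the efficacy analysis and should be corrected because the remedy is simple.

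**What to change.** 1. **Table 1:** change the timing of adverse-effect recording from Visit 2 to Visit 2 or early exit, and add the item to the list in Section 6.2.2.
2. **Section 5.4:** for every early leaver, whatever the main reason, require the Study Questionnaire to state whether an adverse effect occurred and, if so, the event, onset, maximum intensity, relationship and outcome, as known when the exit is learned of. The entry in the patient records can remain as well.
3. **Section 9:** make the copy of each report to the Organizer mandatory, align Section 3.2 with it, and require reconciliation of these reports with the database before the Section 10.4.3 tables are produced.

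The cost is a few extra questionnaire lines for a minority of children and one reconciliation step. No extra visit or procedure is needed. A child who is lost without any contact will still lack data, a limitation that Section 10.5 already acknowledges.

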6. METHODOLOGY

6.1. Schedule of the Study

A summary of observations and assessments that will be conducted during the study is presented in the following table.

Table1. Schedule of the assessments during the Study realisation

PROTOCOL FOR A NON-

INTERVENTIONAL

STUDY

Procedures for particular assessments	Visit 1*	Visit 2*
Demographic data	Х	
Qualification of the Patient into the PAES Study (inclusion criteria)	Х	
History concerning comorbidities and their treatments	Х	Х
Basic diagnosis and its duration	Х	
The dose of the medicinal product used		Х
The assessment of :		
 The symptoms associated with the respiratory system (BSS scale) 		
Assessment of the body temperature	Χ	Х
Assessment of the overall wellbeing (VAS scale)		
Assessment of the sleep quality disturbances		
The use of concomitant treatment		
Duration of the infection (number of days)		Х
Reporting adverse effects related to the HEDUSSIN ® medicinal product use		Х

^{*}The assessments will take place as part of the routine Patient observation

6.2. Assessments in a specialist and primary care clinics under the study

6.2.1. Initial visit (Visit 1) - (day 0)

The Study Questionnaire of Patients using the **HEDUSSIN®** medicinal product, in accordance with the leading physician as well as in accordance with the marketing authorization criteria, shall contain the following information:

- patient number;
- patient initials;
- demographic data;
- interview data on comorbidities;
- initial diagnosis;
- data on the long-term medicine administration in the treatment of comorbidities;
- decision on the Patient's compliance with the inclusion criteria and noncompliance with the exclusion criteria;
- data on the recommended dose of the HEDUSSIN® medicinal product;
- the assessment of the following symptoms:
 - 1. cough severity (from 0 to 4)
 - 2. dyspnoea (from 0 to 4)
 - 3. auscultatory changes during the cough (from 0 to 4)
 - 4. chest pain during the cough (from 0 to 4)
 - 5. hoarse breathing (from 0 to 4)
 - *in accordance with the 5-level BSS scale (Bronchitis Severity Scale) where:
 - 0- absent; 1- mild; 2- moderate; 3- severe; 4- very severe

Study number: EUP/HED/008/2016

VERSION DATE: 21.11.2016

- assessment of the body temperature;
- evaluation of the weakness feeling* *on a 5-level estimation scale where: 0- absent; 1- mild; 2- moderate; 3- severe; 4- very severe
- assessment of the overall wellbeing using the VAS scale;
- assessment of the sleep quality disturbances;
- the used concomitant treatment.
- 6.2.2. Visit 2 (approximately 7-10 days after the previous visit) in accordance to the schedule resulting from the clinical needs of the Patient

The Patients will be present on the control visits in the study centre at the scheduled time. During these visits, the Investigator will collect and record in the Study Questionnaire (SQ) the following information:

Duration of the infection (number of days until the symptoms receded)

A secondary conducting of:

- The assessment of the symptoms associated with the respiratory system on the basis of the BSS scale
- The evaluation of the body temperature
- The assessment of the weakness feeling on the basis of a 5-level estimation scale
- The assessment of the wellbeing based on the VAS scale
- The assessment of the sleep quality disturbances
- The used concomitant treatment

The Patient Observation last approximately 10 days.

7. ASSESSMENTS PERFORMED IN THE STUDY

The Study assumes the assessment of the efficacy of the treatment with the HEDUSSIN® medicinal product.

7.1. Endpoints and the methods of their evaluation

7.1.1. Assessment of the efficacy of the treatment

> Data on the current clinical status of the Patient will be collected during the 2 visits scheduled in the Study Protocol. The efficacy will be assessed on the basis of the assessment of the intensity of the symptoms associated with the respiratory system, the overall wellbeing of the Patient, the duration of the infection and the duration of the WET cough on the day of the first and second assessment.

8. STUDY DRUG

8.1. Administration of the drug

PROTOCOL FOR A NON-

INTERVENTIONAL

STUDY

The HEDUSSIN® medicinal product will be used based on a recommendation from the doctor leading the treatment, after the product is purchased at a public pharmacy. The inclusion of the patient into the group where the given treatment method is used should not result from the study protocol. It should be dependent solely on the current medical practice and remain in accordance with the current medical knowledge.

Study drug

It is a preparation containing the dry extract of common ivy leaves as the active substance.

Excipients: non-crystallizing liquid sorbitol, potassium sorbate, xanthan gum, anhydrous citric acid, purified water

Pharmaceutical form: syrup

Potency: 100 ml of the syrup contains 825 mg of the dry extract of ivy leaves

Name and address of the manufacturer responsible for batch release: Phytopharm Kleka S.A.

8.2. Patient identification

Throughout the duration of the Study all of the included patients must be identifiable. The investigator will maintain the list of the numbers of patients as well as their names and surnames, so that the records can be reached in the future, if necessary. The list of Patients participating in the Study should be kept confidentially at the study centre.

Patient number will be assigned during the first assessment in accordance with the chronological order of inclusion in the study in the resort. Patients in the course of this study will be identified using a unique identification number. Patient number and centre number will be recorded in the Study Questionnaire.

Patients qualified for the study are not covered by randomization.

8.3. Drug delivery

Not applicable.

8.4. Concomitant medication

Data on other drugs used concomitantly with the HEDUSSIN® medicinal product will be recorded in the Study Questionnaire (SQ) during each control assessment.

9. REPORTING RELATED ADVERSE EFFECTS

If a related adverse event occurs, the Investigator is obliged to report each observed event by completing the DRUG RELATED ADVERSE EVENT REPORT and sending it in accordance with the Law on Medicinal Products to:

Phytopharm Kleka S.A. And

URPL

Study number: EUP/HED/008/2016

VERSION DATE: 21.11.2016

Should any severe adverse drug reaction occur, these should be reported within 24h.

The Investigator may additionally report the drug related adverse event to the Study Organizer through the **www.dzialanianiepozadane.com** website. The events reported to the Study Organizer via the abovementioned platform are forwarded to the URPL.

The addresses of all parties are available below:

Phytopharm Kleka SA, [name]

[name] and [name] (deputy) — Persons responsible for the pharmacotherapy safety on behalf of the Sponsor.

e-mail: [contact]

[contact]

Department for Monitoring of Adverse Action Medicines, Office for Registration of Medicinal Products, Medical Devices and Biocidal Products (URPL)

[name]

[name]

tel.: [name]

fax: [name]

e-mail: [contact]

Study Organizer Office: Europharma M.Rachtan Sp.z o.o.

[name]

Reporting via the platform: www.dzialanianiepozadane.com

The procedure for reporting ADR will be carried out in accordance with the standards of GVP

Reporting of adverse reactions associated with the use of the **HEDUSSIN**® medicinal product will be carried out in accordance with the provisions of the Pharmaceutical Law, in particular with art. 45 of the Act on professions of physicians and dentists.

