2. THE AIM OF THE STUDY

2.1. The main aim of the Study

The assessment of the efficacy of the **HEDUSSIN**® medicinal product use in the treatment of productive (wet) cough evaluated on the basis of the severity and the treatment time of the infection occurring with a productive (wet) cough of various aetiologies in children aged 2-12.

The assessment of the efficacy of the **HEDUSSIN®** medicinal product will be based on:

- 1. Observation of the below symptoms and changes in their intensity during the treatment*:
 - The severity of the cough (from 0 to 4)
 - Dyspnoea (from 0 to 4)
 - Auscultatory changes (wheezing, dry rale, crackles) (from 0 to 4)
 - Chest pain during cough (from 0 to 4)
 - Hoarse breathing (from 0 to 4)

0- absent; 1- mild; 2- moderate; 3- severe; 4- very severe

- 2. Determination of the infection duration (measured in days)
- 3. Evaluation of the body temperature
- 4. The use of concomitant treatment:
 - The inclusion of an antibiotic
 - The inclusion of other medications and dietary supplements

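### The 24-hour reporting limit and one safety table depend on the word severe, which is undefined for reactions and elsewhere an intensity grade; no seriousness category exists

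*Protocol*

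**What the plan says.** Section 9 has two layers. The general duty covers every related event: "the Investigator is obliged to report each observed event by completing the DRUG RELATED ADVERSE EVENT REPORT", sent to the marketing authorisation holder and the URPL. No time limit is attached to it. The urgent duty is one sentence: "Should any severe adverse drug reaction occur, these should be reported within 24h". The section also says "The procedure for reporting ADR will be carried out in accordance with the standards of GVP" and refers to the Pharmaceutical Law. It reproduces no definition or deadline from either.

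Section 10.4.3 plans the safety tables:
- The frequency tables have two categories: "The prevalence of all reported adverse effects and severe adverse effects occurring during the study will be presented in the form of tables".
- Inclusion is unrestricted: "All adverse effects occurring during the use of the study drug will be noted in the tables of adverse effects".
- Further "summary tables will be presented, that will include data the maximum intensity of the adverse effect", along with relationship to the drug and discontinuations because of adverse effects.

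The only definition of severe is the symptom scale in section 2.1, "0- absent; 1- mild; 2- moderate; 3- severe; 4- very severe", which is repeated in sections 2.2 and 6.2.1.

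**The concern.** Intensity and seriousness are different attributes of a reaction. Intensity says how strong it is. Seriousness says what it led to or threatened, such as death, danger to life, hospital admission or lasting disability. An urgent reporting rule is meant to follow seriousness. Here the rule uses a word that the protocol defines only as a degree of intensity.

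The literal reading is a realistic one for a site. Dyspnoea is listed in section 1.2 among the allergic reactions to the product, and it is also one of the symptoms that the same investigator grades 0-4 at both visits. An investigator who has just graded a child's dyspnoea as moderate has reason in the text to think that the 24-hour rule is not met, even if the child was admitted to hospital. Conversely, intense but harmless vomiting satisfies the words.

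At stake are the timeliness of reports in children aged 2-12 and the ability of the final report to say how many reactions were serious. The protocol offers little that would catch a misclassification later. Audits, source data verification and a management committee are each marked not applicable (sections 12.1, 12.3, 12.6), and Table 1 schedules the reporting of adverse effects at Visit 2 only.

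**Working it through.** The protocol gives no figure on this point other than the 24-hour limit, so there is nothing to recompute. The check is a reading of every use of the relevant words, followed by applying the rule to each type of reaction.

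**Step 1: what severe means in this protocol.**
- Sections 2.1, 2.2 and 6.2.1: grade 3 of 0-4, one below very severe. The scale is for respiratory symptoms and for tolerance items such as weakness. It is not stated to apply to adverse reactions.
- Section 1.1: one ordinary descriptive use, about the clinical course of inherited disease.
- Section 10.4.3: for effects already present before the first dose, the test is that the effect existed "but its severity has been increasing during the observation". Here severity of an adverse effect means degree.
- Sections 9 and 10.4.3: the two uses at issue, both without a definition.

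**Step 2: whether seriousness appears under any name.** It does not. No adverse-event category called serious exists, and no criterion such as death, threat to life, admission or disability is given.

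**Step 3: apply the text literally, with severe as an intensity grade.**

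| Reaction | Must be reported | 24-hour limit | In all-effects tables | In severe table | In maximum-intensity table | Identified as serious |
|---|---|---|---|---|---|---|
| Serious, mild or moderate | Yes | No | Yes | No | Yes, as mild or moderate | No |
| Serious, severe | Yes | Yes | Yes | Yes | Yes | No |
| Not serious, severe | Yes | Yes | Yes | Yes | Yes | n/a |
| Not serious, mild or moderate | Yes | No | Yes | No | Yes | n/a |

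**Step 4: apply the other reading, with severe standing for serious.** The first row changes to yes for the 24-hour limit and the severe table. The third row changes to no for both. The second and fourth rows keep their entries for the limit and the severe table. The two readings therefore disagree for exactly the reactions whose intensity and seriousness diverge. Under this reading a site still has no criteria by which to decide.

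**Step 5: whether the outside references settle it.** Section 9 invokes GVP and the Pharmaceutical Law in general terms. The protocol does not state what they require, so the reader of the protocol is left with the specific sentence and its word.

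**The case against.** Four points on the other side have weight.

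**Nothing goes unreported.** Section 9 requires a report of every related event, and section 10.4.3 puts all adverse effects into tables. A reader might infer that a serious but non-severe reaction escapes reporting or the summary tables. The documents contradict that. What is lost is the protocol's 24-hour limit and the identification of the case as serious.

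**GVP and the law may set their own deadline.** This stands as a limit on the claim. It cannot be said that urgent reporting would fail in practice, only that the protocol's own text does not secure it. A general reference does not correct a specific instruction that names a different trigger.

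**Severe may simply be a translation of serious.** This is plausible. Section 10.4.3 lists maximum intensity in addition to severe adverse effects, which would be largely redundant if both meant intensity, and the 0-4 scale is never applied to reactions. So an intensity trigger is not proven to be what was intended. The same edit is needed either way: if serious was meant, the wrong word is used and the criteria are absent; if intensity was meant, the trigger is wrong.

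**The report form is not shown, and table details may be left to an analysis plan.** This also stands. One cannot say that the form lacks a seriousness field, or that the study team could never recover the count. It remains true that no table named in the protocol separates serious reactions.

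A reader might also try to size the problem from section 1.2, where allergic reactions are placed at 1/1000 to below 1/100. With 500 children that gives 500 × 0.001 = 0.5 to 500 × 0.01 = 5. But this counts all expected allergic reactions, including hives and rash. The protocol gives no share that would be serious yet non-severe, so the range does not measure the defect.

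**Conclusion.** The point holds as a defect of definition in the protocol's only time-limited safety instruction, carried over into one planned table. Taken literally, a serious reaction of mild or moderate intensity is reported without a stated deadline, appears in the all-effects tables, is missing from the severe table, and is identified as serious in none. A severe but harmless reaction is sent urgently.

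The number of children affected cannot be estimated from the documents. Section 10.4.3 makes the adverse-effect analysis auxiliary to efficacy, and no efficacy result is touched. The case for correcting it rests on the role of the sentence and the small size of the edit.

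The conclusion assumes that a site works from the protocol text and does not supply a seriousness definition from elsewhere. It does not depend on which meaning the authors intended.

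**What to change.** - **Section 9:** replace severe with serious in the 24-hour sentence, and state the seriousness criteria there in line with the GVP standards that the protocol already invokes.
- **Section 10.4.3:** replace severe adverse effects with serious adverse effects in the frequency tables, and keep maximum intensity as its own table.
- **Report form:** check that it records seriousness separately from intensity, and add the item only if it is absent.

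The cost is a wording change in two sections and one check of a form. The small downside is that some serious but non-severe cases must be sent within 24 hours.
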